7.3 Height and Weight

Height or length (cm), and weight (kg) measurements will be taken once. All data will be recorded on the eCRF.

7.4 Head Circumference

Head circumference will be measured once. The data will be recorded on the eCRF.

7.5 Vital Signs

Vital signs (blood pressure, heart rate, respiratory rate, and temperature measurements) will be measured and recorded on the eCRF.

7.6 Electrocardiography

7.6.1 Electrocardiograms

An ECG will be performed. Each ECG will include assessment of heart rate, sinus rhythm, atrial or ventricular hypertrophy, PR, QRS, QT, and QTc intervals. The ECGs will be conducted in accordance with the clinical site's standard practice(s), and will be read locally at the clinical site. Identification of any clinically significant findings and/or conduction abnormalities will be recorded on the eCRF.

7.7 Clinical Laboratory Tests

Blood, urine, and CSF samples will be collected as described below for clinical laboratory testing. Procedures for collection and handling of samples are included in the Laboratory and/or Study Operations Manual.

Patients will be in a seated or supine position during blood collection. Clinical laboratory tests will include hematology, serum chemistry, and urinalysis.

Laboratory Parameters

Clinical laboratory tests will be performed at a central laboratory include the following:

7.7.1 Hematology

- Hematocrit (Hct)
- Hemoglobin (Hgb)
- Mean corpuscular hemoglobin (MCH)
- Mean corpuscular hemoglobin concentration (MCHC)
- Mean corpuscular volume (MCV)
- Platelet count
- Red blood cell (RBC) count
- White blood cell (WBC) count with differential

7.7.2 Serum Chemistry

7.7.2.1 Standard Serum Chemistry

- Albumin (ALB)
- Alkaline phosphatase (ALK-P)
- Alanine aminotransferase (ALT; SGPT)
- Aspartate aminotransferase (AST; SGOT)
- Blood urea nitrogen (BUN)
- Calcium (Ca)
- Carbon dioxide (CO₂)
- Chloride (Cl)
- Creatinine
- Creatine kinase (CK) and subtypes
- Gamma-glutamyl transferase (GGT)
- Globulin
- Glucose
- Lactate dehydrogenase (LDH)
- Phosphorus
- Potassium (K)
- Sodium (Na)
- Total bilirubin
- Direct bilirubin
- Total cholesterol
- Total protein
- Triglycerides
- Uric acid

7.7.3 Urinalysis

Patient catheterization may be required for obtaining urine samples (if deemed necessary by the Investigator).

7.7.3.1 Standard Urinalysis

The following urinalysis parameters will be performed at a central laboratory on urine samples:

- Macroscopic examination
- Microscopic examination of sediment
- pH

7.7.3.2 Urine Heparan Sulfate and Heparan Sulfate Derivatives

A urine sample will be collected for the determination of heparan sulfate and heparan sulfate derivatives and the analysis will be performed at Shire HGT laboratories. A urine sample from each visit will be reserved for possible, exploratory biomarker studies that may provide new indicators or markers of MPS IIIA disease severity or progression.

7.7.4 Cerebrospinal Fluid Assessments

Cerebrospinal fluid (CSF) samples (10 ml in two 5 ml aliquots; labeled separately and processed according to the study operations manual) will be obtained from patients through an implanted IDDD. Should the IDDD become blocked or undergo mechanical complications, the CSF sample will not be obtained via lumbar puncture (LP), except when part of the EOS visit. The performance of LP is at the discretion of the Investigator. See [Section 6.4](#) for further details.

CSF sample collection, processing, and shipping instructions will be provided in the Laboratory and/or Study Operations Manual. A CSF sample will be reserved for possible exploratory biomarker studies for MPS IIIA disease.

Each CSF sample collected will be assessed for appearance and will be analyzed using the assays listed in Sections 7.7.4.1, 7.7.4.2, and 7.7.4.4. In addition, as more is learned about Sanfilippo CNS pathology and etiology, future exploratory assays of CSF metabolites or protein or RNA may become available in the future (the samples maybe analyzed, if the assays are found applicable) and are thus not presently listed within this protocol.

7.7.4.1 CSF Cell Counts

An aliquot of each CSF sample collected will be evaluated for CSF standard chemistries, glucose, protein, and cell counts. These assessments will be performed at the local laboratory.

7.7.4.2 CSF Heparan Sulfate Levels and Heparan Sulfate Derivatives

An aliquot of each CSF sample collected will be quick frozen as per the Laboratory and/or Study Operations Manual for subsequent determination of CSF heparan sulfate and heparan sulfate derivatives at Shire HGT laboratories.

7.7.4.3 Anti-rhHNS Antibodies

An aliquot of each CSF sample collected will be quick frozen as per the Laboratory and/or Study Operations Manual for subsequent determination of anti-rhHNS antibodies at Shire HGT laboratories.

7.7.4.4 CSF Biomarkers

An aliquot of each CSF sample collected will be quick frozen as per the Laboratory and/or Study Operations Manual for subsequent determination of MPS exploratory biomarkers at Shire HGT laboratories.

7.7.5 Sample Collection, Storage, and Shipping

Sample collection, processing, and shipping instructions will be provided in the Laboratory and/or Study Operations Manual to be provided by Shire HGT.

7.8 Anesthesia

Administration of anesthesia/sedation will be given prior to obtaining CSF (when the use of the IDDD is precluded – see [Section 6.4](#)), prior to performing the MRI of the head, the ABR, the intracranial pressure (ICP), and the re-implantation of the IDDD (if applicable). See [Appendix 1](#) for the Schedule of Events.

Note: the neurologic exam and the neurocognitive and developmental assessments must be performed prior to the administration of anesthesia.

7.9 Audiometry and Auditory Brainstem Response

The rare attenuated patients with MPS IIIA with high levels of cognitive functioning will have hearing tests via clinical audiometry measurement performed using age-appropriate testing methods based on the child's developmental age at the time of the testing. It is anticipated that most of the cognitively-impaired and/or behaviorally-deteriorated patients with Sanfilippo A will be unable to co-operate with a (conscious) hearing evaluation. In these instances, the Investigator will utilize his best clinical judgement to initially estimate the extent of hearing loss (if any) during the initial physical examination. In this situation, specific evaluation of hearing loss will await examination of waveforms in the ABR (see below). If the patient has a history of multiple instances of otitis media or evidence of clinically-significant otitis media on physical examination, which the Investigator believes causes significant conductive hearing loss and impairment of daily living, the Investigator will ask and offer the parent or guardian placement of PE tubes as part of the scheduled anesthesia. A patient's PE tubes may be replaced if they fall out during the course of this study.

The auditory brainstem response (ABR) will be conducted under anesthesia. The ABR findings will be considered within normal limits if, after applying appropriate correction factors, the waveforms reveal normal morphology.

7.10 MRI of the Head

The regional brain volume will be assessed through an MRI of the head. The patient will be under general anesthesia for this assessment. The central reading for MRI data, across all sites, will be completed at the University of Minnesota Medical Center. Refer to the Study Operations Manual for specific procedures and precautions.

7.11 Surgical Re-implantation of the IDDD

If a patient's IDDD becomes nonfunctional or infected, it will be replaced so that the patient can remain on study. Procedures for implantation will be detailed in the device's Instructions for Use manual. The patient will be under general anesthesia for this procedure. Standard hospital procedure for surgery will be followed and will include an X-ray to confirm device placement at the mid-thoracic level. A post-operative check of the IDDD will be performed on Day 7 following surgery. X-rays may be performed to check placement of the device, as needed, throughout the study. Drug can only be administered via the IDDD.

7.12 Intracranial Pressure Measurement

Intracranial pressure measurement (ICP) (centimeters of H₂O) will be conducted per standard hospital practice. The measurement will be obtained whenever a LP is performed.

7.13 Dispensing Study Drug

rhHNS will be administered IT by means of an IDDD to patients in Dose Groups 1 and 2 on Day 2 (± 2 days) of Week 1 of each treatment month and to patients in Dose Group 3 on Day 2 (± 2 days) of Weeks 1 and 3 of each treatment month.

The patient may be mildly sedated for this procedure; rhHNS will be administered over 2 to 5 minutes. Please see [Section 6.5](#) if the IDDD is not functioning.

The patient must not receive aspirin, non-steroidal anti-inflammatory medications, or medications that affect clotting within 1 week prior to each IT injection.

7.14 Pharmacokinetic Assessments

Pharmacokinetic assessments will not be included in this study.

7.15 Neurological Examination

A neurological examination to monitor CNS changes in patient's neurological status will be conducted during this study. See [Appendix 2](#) for a complete list of the neurological examinations.

7.16 Serum Anti-rhHNS Antibody, Heparan Sulfate and Heparan Sulfate Derivative Determination

Blood samples will be collected prior to rhHNS injection and evaluated at Shire HGT laboratories for the determination of anti-rhHNS antibodies, heparan sulfate and heparan sulfate derivatives. Samples will be reserved for potential future MPS IIIA research that may determine biomarkers of disease severity and progression.

Two 5 mL blood samples will be collected from each patient at each designated time point. One 5 mL sample will be collected in a tube intended for serum specimens, while the second sample will be collected in a tube intended for plasma specimens. Blood sample collection, processing, and shipping instructions will be provided in the Laboratory and or Study Operations Manual.

7.17 Neurocognitive and Developmental Assessments

Patients will undergo neurocognitive and neurobehavioral development testing. The assessments are estimated to last between 2 and 4 hours and must be conducted prior to sedation or anesthesia.

A full neurodevelopmental assessment, including global development, cognition, adaptive behavior, receptive and expressive language, and gross motor function, will be evaluated using standardized developmental and behavioral tests to provide a surrogate and quantifiable measure of global CNS neurodevelopmental/neurobehavioral function.

For this study, outcome measures will be computed for each patient enrolled. The psychometric instruments and Sanfilippo-specific assessments are summarized below in Table 7-2 and Table 7-3, respectively. See Appendix 3 for details on these assessments.

Table 7-2 Neurodevelopmental Assessments Tests

Developmental or Cognitive Domain(s)	Patient Age: Representative Cognitive Test or Scale
COGNITIVE DEVELOPMENT ASSESSMENT	
Summary score and sub-domains:	0 to 42 months: Bayley Scales of Infant Development-III (BSID-III) ²³
- Cognitive	
- Motor	
- Cognitive	3 to 18 years: Kaufman Assessment Battery for Children, Second Edition (KABC-II) ²⁴
- Processing skills	
GROSS AND FINE MOTOR SKILLS ASSESSMENT AND VOLUNTARY MOVEMENT	
Motor	3.0 to 16:11 years: Movement Assessment Battery for Children II (MABC-2) ²⁵
- Cognitive	0 to 5 ½ years: Bayley Scales of Infant Development III (BSID-III) ²³
- Motor	

Table 7-2 Neurodevelopmental Assessments Tests

Developmental or Cognitive Domain(s)	Patient Age: Representative Cognitive Test or Scale
ADAPTIVE BEHAVIOR	
Communication	0 to 90 years: Vineland Adaptive Behavior Scales (VABS-II) Second Edition ²⁶
Daily Living	
Socialization	
Motor Skills	

Table 7-3 Sanfilippo-Specific Disability Assessment And Behavior Rating Scales

Developmental or Cognitive Domain(s)	Sanfilippo Specific Assessments
Parent-scored behavioral inventory - communication: understanding - communication: expression - tantrums - specific behaviors inventory - mood & emotions inventory	Sanfilippo Behavior Rating Scale (SBRS)
MPS-specific disability score - cognitive functioning - expressive language - motor score	Four-Point Scoring System/Total Disability Score (FPSS/TDS) ⁴

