Patients whose parents/legal guardians provide written informed consent/assent to participate in this study will check in with the study center 1 day prior to rhHNS dosing for safety assessments on each rhHNS treatment week. If no safety concerns exist, the patient will subsequently receive IT administration of rhHNS on Day 2 (± 2 days). Patients will be discharged from the inpatient unit a minimum of 1 day following dosing with rhHNS and when deemed clinically stable by the Investigator.

The patient will have already received a standardized battery of neurodevelopmental assessments at the Baseline and 6-month time points in the HGT-SAN-055 study. These same assessments and tests will be performed at 12, 24, 36, and 48 months. Similarly, MRI of the head, ABR testing, CSF sampling by means of lumbar puncture and any other procedures requiring anesthesia will be performed at 12, 24, 36, and 48 months.

All patients will undergo end of study procedures 30 (\pm 7) days following their last administration of rhHNS. End of study procedures will include a standard battery of clinical laboratory tests (serum chemistry, hematology, and urinalysis) in CSF and blood, protocol specific laboratory testing (eg, anti-rhHNS antibody testing), neurodevelopmental testing, ABR, child health questionnaires, MRI, and concomitant medications and AE monitoring.

All patients will be contacted by telephone for a Final Safety Follow-up, to be conducted at 30 (\pm 7) days after the EOS procedures to collect updated information on adverse events and concomitant medications, therapies, and procedures.

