4.2 Rationale for Study Design and Control Group

Study HGT-SAN-055 is an ongoing Phase I/II safety and ascending dose ranging study of intrathecal administration of rhHNS via an IDDD, in patients 3 years of age and older with MPS IIIA and early cognitive impairment. This extension study is proposed to continue evaluation of the effects of intrathecal rhHNS administration on long-term safety and clinical outcomes for patients who completed Study HGT-SAN-055 and elected to continue treatment with rhHNS.

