7.19.3 Quality of Life Indicator: ITQOL

The Infant Toddler Quality of Life Questionnaire™ (ITQOL) will be administered during the study. The ITQOL was developed for children at least 2 months of age up to 5 years and assesses the physical, mental, and social well being of the child and assesses the quality of the parent/guardian's life.

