10.6.2 Secondary Analysis

10.6.2.1 Clinical Assessments

The change from baseline in neurocognitive assessment based scores will be examined by dose group. Furthermore, the effect of rhHNS administration on QoL measures will be examined by presenting mean change from baseline across dose groups. Other relevant assessments which might help in the understanding of clinical activity will also be analyzed.

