Appendix 3 Neurodevelopmental and Behavioral Assessments

Table 3-1 and Table 3-2 detail the specific psychometric instruments that will be used to provide measures of each of relevant neurobehavioral or developmental domain assessed. The tables also summarize the rules used to select a test for a patient, the subtests included in each test, and the subscales generated by the test battery.

Table 3-1 Summary of Neurodevelopmental Outcome Measures

Domain	Age	Test
Summary score and subdomains: - Cognitive - Motor	0 to 42 months	Bayley Scales of Infant Development, Third Edition (BSID-III) ²³
- Cognitive - Processing skills	3 to 18 years	Kaufman Assessment Battery for Children, Second Edition (KABC-II) ²⁴
Motor	3.0 to 16:11 years	Movement Assessment Battery for Children, Second Edition (MABC-2) ²⁵
Communication Daily Living Socialization Motor Skills	0 to 90 years	Vineland Adaptive Behavior Scales, Second Edition (VABS-II) ²⁶

Table 3-2 Summary of Sanfilippo-specific Assessments

Domain	Assessment
Parent-scored behavioral inventory - communication: understanding - communication: expression - tantrums - specific behaviors inventory - mood & emotions inventory	Sanfilippo Behavior Rating Scale
MPS-specific four-point scoring system/total disability score - cognition - expressive language - motor score	Four-Point Scoring System/Total Disability Score (FPSS/TDS) ⁴

The term “neurodevelopmental” refers to the process by which the neurological system matures and changes over time. Assessing these changes in a population of children whose neurological system is progressively more affected can be very challenging.

Typically, neurodevelopmental progress is reflected by the child’s abilities to perform certain skills (sitting, walking, and talking). However, a child with a neurological disorder may be able to perform age appropriate skills, but with atypical patterns.

For example, the child may be able to walk, but his gait is not normal. Most assessments will therefore measure the skills, but are not designed to capture the abnormalities in pattern or quality of the skill.

These qualitative differences will be evident to the skilled test administrator/clinician who is familiar with the disorder. However, only longitudinal tracking and repeated measures will reveal the significance of these abnormalities in overall function to the less experienced clinician.

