The rate at which different skills develop or regress over time will give insight into the disease process. The next step is to determine how the learned skills are used for daily functional activities so that as the children grow up they become independent from caregivers. These functional skills can be tracked to reflect quality of life issues for both parents and children.

Neurodevelopmental assessments described below will be scheduled for administration in the morning and estimated to last between 2 and 4 hours.

The list of assessments is discussed in detail in the Study Operations Manual and includes:

Bayley Scales of Infant Development, Third Edition (BSID-III)²³

The Bayley Scales of Infant Development is a standard series of measurements used primarily to assess the motor (fine and gross), language (receptive and expressive), and cognitive development of infants and toddlers, ages 0 to 42 months. This measure consists of a series of developmental play tasks and takes between 45 and 60 minutes to administer. Raw scores of successfully completed items are converted to scale scores and to composite scores. These scores are used to determine the child's performance compared with norms taken from typically developing children of their age (in months). The assessment is often used in conjunction with the Social-Emotional Adaptive Behavior Questionnaire. Completed by the parent or caregiver, this questionnaire establishes the range of adaptive behaviors that the child can currently achieve and enables comparison with age norms.

Kaufman Assessment Battery for Children, Second Edition (KABC-II)²⁴

Purpose:

The KABC-II measures a child's cognitive ability and processing skills and was designed to minimize verbal instructions and responses. In addition, the assessment contains little cultural content to provide a more accurate assessment of children from diverse backgrounds. Thus language difficulties or cultural differences are minimized in the test battery's results.

Description:

Investigators may choose either the Cattell-Horn-Carroll or the Luria model for a patient's assessment.

The Cattell-Horn-Carroll model is used with children from a mainstream cultural and language background and the Luria model is used for children with significantly limited verbal ability. Subtests are administered on four or five ability scales and interpreted using the chosen model.

Movement Assessment Battery for Children, Second Edition (MABC-2)²⁵

Purpose:

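### Table 7-2 gives BSID-III two conflicting age ranges that overlap KABC-II without a tie-break, and nothing keeps a child on one cognitive test or KABC-II model across visits

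*Protocol*

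**What the plan says.** Section 7.17, Table 7-2, lists the cognitive test by patient age. For the youngest it gives "0 to 42 months: Bayley Scales of Infant Development-III (BSID-III"; for ages 3 to 18 years it gives KABC-II. In the motor block of the same table BSID-III appears again, listing both Cognitive and Motor, with a range of 0 to 5 1/2 years. Table 3-1 in Appendix 3 carries only the 42-month range, and the appendix says of its tables: "The tables also summarize the rules used to select a test for a patient".

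Within KABC-II, Appendix 3 states that "Investigators may choose either the Cattell-Horn-Carroll or the Luria model". It directs the first model to children of mainstream culture and language and the second to children whose verbal ability is markedly restricted.

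Section 4.2 describes HGT-SAN-055 as a study "in patients 3 years of age and older with MPS IIIA and early cognitive impairment". Baseline for the extension is the day of the first intrathecal dose in that study (Section 8.1). Section 4.1 says of the battery given at baseline and 6 months: "These same assessments and tests will be performed at 12, 24, 36, and 48 months". Section 10.6.2.1 then plans: "The change from baseline in neurocognitive assessment based scores will be examined by dose group".

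**The concern.** A change score is interpretable only if the same thing is measured at both ends. Here the rule that selects the instrument is inconsistent, so two sites could follow Table 7-2 correctly and give the same child different tests. Because the rule depends on age, it can also move a child from one test to another during follow-up.

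The KABC-II model adds a second route. Section 1.1 names language deficit as a feature of the disease, so a criterion based on verbal ability is related to the outcome being measured. If a child loses speech, the text would allow a change of model, and part of the measured change would then come from the instrument.

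This is a data-collection matter. Once baseline and follow-up have been recorded on different tests, no later analysis can recover a same-test difference.

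**Working it through.** The protocol states no effect size, SD or power for these scores, so there is no figure of its own to reproduce. The check is age arithmetic.

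Inputs:
- Minimum age at baseline: 36 months (Sections 1.3 and 4.2).
- Extension testing at Months 12, 24, 36 and 48 from that baseline; Month 6 fell in the parent study (Section 4.1).
- BSID-III upper limits: 42 months, and 5 1/2 years = 66 months (Table 7-2).
- KABC-II lower limit: 3 years = 36 months (Table 7-2).

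**Overlap.** BSID-III and KABC-II are both available from 36 to 42 months on the narrow range, or from 36 to 66 months on the wide one.

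**Ageing out.** Age at visit = baseline age + months since baseline. Ages are whole months and the limit is inclusive.

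| Baseline age (months) | Last visit in range, limit 42 | Last visit in range, limit 66 |
|---|---|---|
| 36 | Month 6 (42) | Month 24 (60) |
| 42 | Baseline (42) | Month 24 (66) |
| 48 | not eligible | Month 12 (60) |
| 54 | not eligible | Month 12 (66) |
| 60 | not eligible | Month 6 (66) |
| 66 | not eligible | Baseline (66) |

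The youngest possible patient sets the bound:
- Limit 42: 36 + 12 = 48 > 42, so no patient is in range at any scheduled extension assessment.
- Limit 66: 36 + 36 = 72 > 66, so no patient is in range at Month 36 or Month 48.

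Under either limit, a child who starts on BSID-III and is tested by the age rule has no same-test change from baseline at Month 48.

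**Who is affected.** Forced changes are confined to children given BSID-III at baseline: aged 36 to 42 months, or up to 66 months on the wider range. The documents do not give that number. It lies between 0 and 12, the maximum enrolment in Section 10.2. If the 12 were spread evenly over three dose groups (an assumption), each group would have 4 patients, and one child with mismatched tests would carry 1/4 of a group mean.

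**KABC-II model.** Section 7.17 and Appendix 3 contain criteria for the choice of model but no sentence requiring the same choice at later visits. A switch is permitted, not prescribed.

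**The case against.** The strongest reply is that no change of test need occur. Every patient is at least 36 months old and therefore eligible for KABC-II from the start. Baseline testing was done under HGT-SAN-055, whose protocol is not shown, and perhaps nobody took BSID-III. The promise in Section 4.1 can be read as referring to a battery that itself contains age-banded tests. This stands as a limit on how many children are affected. It does not remove the two printed ranges or the missing tie-break.

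The impact is also bounded. Safety is the primary endpoint, the efficacy measures are unranked secondary endpoints handled descriptively, and Section 7.25 says the assessments are partly meant to learn which tools work. VABS-II (0 to 90 years) and the FPSS/TDS (all ages) need no change of instrument.

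A reader might infer three stronger points that the documents do not support:

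- That the planned scores will fall even when skills are stable. An age-normed quotient would: with a constant age equivalent of 24 months, 100 x 24/48 = 50.0 at 48 months and 100 x 24/84 = 28.6 at 84 months. But Section 10.6.2.1 does not say which kind of score is analysed, and the SAP may fix that.
- That KABC-II model switches will be driven by the outcome. The text leaves this possible; it provides for no such switch.
- That quality-of-life forms change with age in the same way. Section 7.19.3 says only that "The ITQOL was developed for children at least 2 months of age up to 5 years", and Appendix 1 schedules ITQOL, CHQ-50 and CHQ-87 together at each annual visit. No passage moves a child from one form to another.

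**Conclusion.** The point holds as an internal inconsistency with a real but limited consequence. Table 7-2 contradicts itself on the BSID-III range, Appendix 3 gives only one of the two ranges as the selection rule, and the overlap with KABC-II is unresolved. For any child who began on BSID-III, the age rule is incompatible with repeating the same tests, from Month 12 on the narrow range and by Month 36 at the latest on the wide one. Nothing holds the KABC-II model constant for the others.

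It would go too far to say that every patient's cognitive change score mixes tests: a child on KABC-II from baseline stays within its range to Month 48 if aged up to 14 years at baseline (14 + 4 = 18). For secondary, descriptive endpoints this is worth correcting but does not threaten the study's primary purpose.

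The conclusion assumes that the age in the tables is chronological age. The word is not printed, but Section 7.9 specifies developmental age for audiometry and Table 7-2 does not. It also rests on the original protocol and Amendment 1 alone. The title page lists Amendments 2 to 8, which are not shown and may have changed this text.

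**What to change.** In Table 7-2 and Appendix 3:

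1. Print one BSID-III age range, and state which test is used where it overlaps KABC-II.
2. State that each patient stays on the cognitive test and the KABC-II model used at the HGT-SAN-055 baseline for every score entering a change from baseline.
3. State that if a test has to change because a child cannot be scored on it, normed scores are not pooled across the two tests, and the age-equivalent score is reported. The quotient alone is not enough, since it falls with age when skills are stable.

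The protocol mentions age equivalents only for VABS-II, so their availability for BSID-III and KABC-II should be confirmed in the Study Operations Manual before item 3 is adopted.

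The cost is amendment and manual wording. The downside is small: a child kept on a test beyond its norm range has no age-normed standard score at those visits.
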